### 11.1.1 Guidelines for Tissue Acquisition on Biopsies of Metastatic Lesions

Tissue specimens, when feasible, will be collected from recurrent or metastatic lesions using standard institutional procedures. The amount of tissue collected will follow the guidelines listed below. If a patient has more than one site of disease, only one site needs to be biopsied, and the site is left to the discretion of the patient and the treating physician. If a patient is undergoing resection of a lesion for clinical reasons (i.e. wedge resection of a new lung lesion for confirmation of diagnosis or re-testing of hormone receptor or HER2 status; or, resection of a chest wall lesion; or, resection of a lymph node), then the patient may opt to have a portion of that tissue (roughly equivalent to the goal amount of tissue listed in the guidelines above, i.e. the equivalent of two 5-mm punch biopsies of the skin, or 3-6 18-gauge core biopsies) stored for research at the time of the procedure.

Listed below are the goal amounts of tissue for patients who undergo core biopsy or punch biopsy, or who have either ascites fluid or pleural fluid accessible for collection. Please note that the below are guidelines for the amount of tissue to be obtained at the baseline biopsy, and are not meant to replace clinical judgment at the time the procedure is performed. Less than the goal quantity of tissue is accepted for each type of biopsy, and will be left to the clinical judgment of the physician performing the procedure.

- Breast: A goal of 3-6 core biopsy specimens will be obtained using standard institutional guidelines for a diagnostic core biopsy of a breast mass
- Skin/chest wall: A goal of one to two 5-mm punch biopsies
- Lymph node: A goal of 3-6 core biopsy specimens will be obtained using an 18-gauge needle
- Liver: A goal of 3-6 core biopsy specimens will be obtained using an 18-gauge needle
- Lung: A goal of 3 core biopsy specimens will be obtained using an 18-gauge needle. Due to the risk of pneumothorax associated with core needle biopsies of lung nodules, peripheral lesions should be carefully selected.

- Bone: Because the yield of malignant tissue from bone biopsies tends to be relatively low, if a patient has another accessible site of disease (i.e. skin, lymph node, liver), that site should be biopsied preferentially. If bone is the only biopsy-accessible site, then a goal of 3-6 core biopsy specimens will be obtained using an 18-gauge needle.
- Pleural Fluid (known or suspected to be due to malignancy): This should only be used if there is no other site noted above that can be biopsied and this should be discussed with the VICC coordinating center. A goal of 500 cc of pleural fluid will be obtained with a standard thoracentesis procedure, with or without image guidance, according to the clinical judgment of the treating physician and clinician performing the procedure. Less than the goal amount is acceptable, and should be based upon the clinical judgment of the Investigator and the clinician performing the procedure. If more than the goal amount of fluid is obtained, then the entire specimen (with the exception of what is needed for clinical purposes, if applicable) will be stored at Vanderbilt.
- Ascites fluid: This should only be used if there is no other site noted above that can be biopsied and this should be verified by the VICC coordinating center. A goal of 500 cc of ascites fluid will be obtained with a standard paracentesis procedure, with or without image guidance, according to the clinical judgment of the treating physician and clinician performing the procedure. Less than the goal amount is acceptable, and should be based upon the clinical judgment of the Investigator and the clinician performing the procedure.

### 11.1.2 Instructions on fresh tissue specimen handling

\*Tissue obtained at Vanderbilt will be handled differently as it does not need to be shipped. Please see the Vanderbilt lab manual for handling if obtaining a biopsy at Vanderbilt\*

- First core biopsy should be suspended in 10% buffered formalin.
- Second core biopsy should be suspended in 5-10 volumes “RNAlater” solution\*
- Third core biopsy should be suspended in 10% buffered formalin.
- Fourth core biopsy should be suspended in 5-10 volumes “RNAlater” solution\*
- Fifth core biopsy should be suspended in 10% buffered formalin

\*RNAlater kits will be provided. 1 core should be placed in one 1.5ml specimen tube. All samples should be shipped immediately, according to the lab manual.

For patients in whom a core biopsy is not possible and who thus undergo fine needle aspiration (FNA), 3 passes should be collected.

- First pass should be evacuated and rinsed directly into 10% buffered formalin
- Second pass should be evacuated and rinsed directly into 5-10 volumes “RNAlater” solution\*
- Last pass should be evacuated and rinsed directly into 10% buffered formalin.

## 11.2 Blood/plasma collection

Streck Cell-Free DNA BCT kits will be provided for circulating tumor DNA. One vial of whole blood should be collected in a Cell-Free DNA BCT tube (Streck tube). Fill the tube completely. Remove the tube from the adapter and immediately mix by gentle inversion 8 to 10 times. Collection times are: cycle 1/day 1, cycle 2/day 1, and end-of-treatment, see study calendar.

Tube should be packed and shipped according to the lab manual and sent immediately (within 24 hours) to VICC at the address provided. **Do not freeze specimens collected in Streck tube.**

## 11.3 Tissue specimen and blood/plasma labeling and documentation

Label each collection containers with Patient ID sequence number/code letter, site and location of biopsy, date and time.

If sample comes in contact with contaminate, make note in information section of paperwork.

Enter time core biopsy was collected on paperwork.

Outside sites should ship specimens along with Tissue Registration Form as directed in the lab manual.

The specimens will be logged in as a consented specimen and available for molecular pathology studies.

## 11.4 Peripheral Blood Mononuclear Cell Collection

Blood will be collected on Cycle 1/ Day 1, Cycle 2/ Day 1, and at the end-of-treatment (also Cycle 1/Day 1, Cycle 2/Day 1, and end-of-treatment for those crossing over to carboplatin + atezolizumab).

BD Vacutainer® CPT™ Mononuclear Cell Preparation Tubes are included to collect blood. One vial of whole blood should be collected in a BD Vacutainer® CPT™ (CPT tube).

Whole blood is drawn directly into the CPT™ using standard phlebotomy techniques and in accordance with the lab manual. Samples should be shipped according to the lab manual.

## 11.5 Genetic Testing

Participants will be given information as part of the informed consent process that samples will be used for research tests that will include genetic studies and testing. The intent is not to give participants (or his/her medical providers) the results of any testing done for research purposes; however, incidental germline (heritable) mutations may be identified of which a participant may or may not already be aware. In the case that an incidental genetic finding is identified, the Protocol Chair of this project will be notified. The possible decisions for handling incidental findings may include notification of the participant (and provider); recommendation for genetic counseling, which may or may not include genetic testing (e.g., if the finding was not done in a CLIA certified laboratory); or, neither. In general, a member of the participant's treating team will be given the information to help with notification. In all cases, the current policy of the Vanderbilt and

local/participating site IRB, as applicable, will be followed and any additional approvals that may be required prior to participant notification will be secured in advance.

### **11.6 Specimen Banking**

Any leftover study tissue or blood samples may be stored for future research studies. The subjects will consent to the future use of samples in the consent form for the study, which includes the transfer of specimens to Genentech for product development. The study PI and collaborators have approval by the TBCRC, which has custodial oversight of all biospecimens collected as part of a TBCRC trial, to address the research questions described in the protocol document. All future use as part of residual or repository specimens collected in this trial for purposes not prospectively defined will require review and approval by the TBCRC according to its established policies, whether the specimens are stored in a central site or at a local institution or in a virtual repository. Secondary use of bio-specimens for new endpoints must be submitted to the TBCRC Central Office for possible review by the TBCRC Correlative Science Review Committee.

### **11.7 Biopsy Questionnaire**

A questionnaire will be given to each participant to complete at cycle 2, day 1. This questionnaire is designed to assess the impact of the biopsy on the patient's quality of life and overall experience with the study.

### **11.8 Imaging Correlative Study**

Evaluation of muscle mass, muscle attenuation, and adipose mass will be determined using baseline abdominal CT scans collected for central review. A transverse cut at the L3 level will be extracted, as muscle and adipose area at this level is linearly related to whole body mass. SliceOmatic software (version 5, Tomovision) will be used to process images, providing a highly accurate estimation of cross-sectional skeletal muscle area and muscle attenuation with high inter-observer reliability. The software is semi-automated and will be run by two independent investigators, with a subset of images read by both investigators to determine a coefficient of variation. Muscle mass, muscle attenuation, and adiposity will be evaluated both as continuous and categorical variables (LMM: yes/no, LMA: yes/no, adipose: tertiles). LMM is defined as skeletal muscle index (SMI, lean muscle area/height, cm^2/m^2) less than 41 and LMA will be defined as average muscle density less than 25 HU, or less than 33 HU if the patient is overweight/obese by BMI. These cut-points are based on previously determined thresholds associated with reduced survival in patients with metastatic solid tumors. We will also explore whether there are alternate cut-points predictive of survival in this particular population based on optimal stratification. Total adiposity will be defined as the sum of visceral adipose tissue, subcutaneous adipose tissue, and intramuscular adipose tissue and evaluated by tertiles.

## **12. MEASUREMENT OF EFFECT**

For the purposes of this study, patients should be re-evaluated for response after every 3 cycles. Response and progression will be evaluated in this study using the international criteria proposed by the revised Response Evaluation Criteria in Solid Tumors (RECIST) Committee (version 1.1). Any evaluable or measurable disease must be documented at screening and reassessed at each subsequent tumor evaluation. For PFS analysis, patients will be considered to have disease progression if their tumor assessment shows PD by RECIST. However, as conventional response

criteria may not adequately assess the activity of immunotherapeutic agents because radiographic progressive disease does not necessarily reflect therapeutic failure, for patients on the carboplatin + atezolizumab arm, if a patient is found to have disease progression by RECIST, at the discretion of the treating physician, the patient may remain on study and managed by irRECIST (see section 12.5) provided he/she meets the following criteria:

- Evidence of clinical benefit as assessed by the investigator.
- Absence of symptoms and signs (including worsening laboratory values [e.g., new or worsening hypercalcemia]) indicating clinically significant progression of disease
- No decline in ECOG performance status that can be attributed to disease progression
- Absence of tumor progression at critical anatomical sites (e.g., leptomeningeal disease) and no other signs/symptoms of unequivocal disease progression. This includes tumor progression that cannot be managed by protocol-allowed medical interventions (ie., pain secondary to disease or unmanageable ascites, etc.), as determined by the investigator after an integrated review of radiographic data and clinical status.

Scans should be repeated after 6 weeks, and if progression is confirmed by irRECIST, the patient should be removed from study. If scans by irRECIST show the patient to not have disease progression, the patient may remain on study after discussion with the Protocol Chair. Patients on the carboplatin alone arm who show progression by RECIST must either be removed from study or cross over to receive atezolizumab.

Conventional response criteria may not adequately assess the activity of immunotherapeutic agents because radiographic progressive disease does not necessarily reflect therapeutic failure. In Phase Ia Study PCD4989g, several patients who progressed per RECIST v1.1 continued on atezolizumab treatment and subsequently demonstrated durable anti-tumor activity. Of the 21 patients with TNBC in the study who were evaluable for response 3 patients with IC2/3 TNBC showed evidence of target lesion shrinkage after an initial increase in tumor burden or following the appearance of new lesions. These patients likely experienced pseudoprogression or delayed response ([Emens et al. 2014](#)). Additionally, in some responding patients with NSCLC in Study PCD4989g, the growth of known lesions or the appearance of new radiographic lesions were shown to contain immune cells and no viable cancer cells on biopsy ([Gettinger et al. 2013](#)). The expected rate of pseudoprogression or delayed anti-tumor immunity when atezolizumab is administered in combination with carboplatin is not known. On the other hand, radiographic progression when carboplatin is given alone is likely to represent true disease progression requiring a change in therapy. Although the primary endpoint measures of efficacy (PFS) will be performed using RECIST v1.1, noncomparative analyses of these measures will be performed with use of immune-modified RECIST for patients who continue treatment beyond radiographic progression. The immune-modified RECIST allows the incorporation of new lesions into the calculation of total tumor burden after baseline.

## 12.1 Definitions

Evaluable for toxicity. All patients will be evaluable for toxicity from the time of their first treatment with atezolizumab and/or carboplatin. Evaluable for objective response. Only those patients who have measurable disease present at baseline, have received at least one cycle of therapy, and have had their disease re-evaluated will be considered evaluable for response. These patients will have their response classified according to the definitions stated below. (Note: Patients who exhibit objective disease progression prior to the end of cycle 1 will also be considered evaluable.)

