### **8.7 Criteria for Removal from Study**

Patients will be removed from study when any of the criteria listed below apply. All patients who initiate protocol treatment will be included in the overall evaluation of response (intent-to-treat analysis). All reasons for discontinuation of therapy should be documented clearly in the medical record.

If a subject discontinues or withdraws from the study, every reasonable attempt will be made to get a tissue/tumor biopsy, along with blood, at the end of treatment, if the subject is able and willing.

Patients may be withdrawn from the study if they experience any of the following:

- Disease progression, per investigator assessment by RECIST (or irRECIST for atezolizumab arm)
- Intolerable toxicity to atezolizumab or carboplatin. Patients assigned to carboplatin + atezolizumab who experience toxicity to atezolizumab or carboplatin can continue on study with single agent carboplatin or atezolizumab, respectively, at the discretion of the treating physician. Patients will be followed for disease progression and should continue radiologic assessments every 3 cycles as per the study.

Other reasons for patient discontinuation may include, but are not limited to, the following:

- Non-compliance with the study protocol, including, but not limited to not attending the majority of scheduled visits. The Protocol Chair will determine when non-compliance should lead to removal from study. Note: The patients will still be included in the overall evaluation of response (intent-to-treat analysis).
- Patient personal decision. The reason for discontinuation from the study must be documented. The patients will be included in the overall evaluation of response (intent-to-treat analysis) if any protocol therapy was administered prior to withdrawal.
- If the patient becomes pregnant
- Patient is lost to follow-up
- Study is terminated for any reason

The investigator has the right to discontinue a patient from the study for any medical condition that the investigator determines may jeopardize the patient's safety if he or she continues in the study; for reasons of noncompliance (e.g., missed doses, visits); or if the investigator determines it is in the best interest of the patient. The Protocol Chair should be notified in such cases.

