## 17.3 Analysis of Secondary and Exploratory Endpoints

We will calculate the ORR, CBR, DOR, and OS and corresponding 95% confidence intervals. PFS, ORR, and DOR will also be analyzed using irRECIST.

RNA-seq will be performed on all biopsies to assign a triple negative subtype, to determine baseline and treatment-induced changes in GE after therapy and define mutations present in the tumors both at baseline and upon progression of the disease. We expect an enrichment of drug resistance-associated mutations/gene amplifications particularly in tumors that regress and later recur while on therapy. Somatic SNPs and structural variants will be validated by whole exome sequencing (WES) of genomic DNA from the tumor and matched blood. We will validate mutations by targeted capture approaches that allow high-level coverage (greater than 200X) and analysis of clonality. The status of p53, BRCA1/2, PIK3CA, PTEN, INPP4B and other mutations associated with TNBC, along with PDL1 expression and TILs in the tumor tissue is critical for testing our hypothesis. We anticipate significant opportunity for discovery of novel mutations as well as those arising from selection during resistance to the therapies under investigation. Statistics on the correlative endpoints (tissue assays) will be primarily descriptive. Therefore, these studies are considered to be exploratory and potentially hypothesis-generating.

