### 17.5 Reporting and Exclusions

All patients included in the study must be assessed for safety, tolerability, and response to treatment, even if there are major protocol treatment deviations or if they are ineligible. Each patient will be assigned one of the following categories: 1) complete response, 2) partial response, 3) stable disease, 4) progressive disease, 5) early death from malignant disease, 6) early death from toxicity, 7) early death because of other cause, or 9) unknown (not assessable, insufficient data).

All of the patients who met the eligibility criteria and received study drugs for 4 weeks should be included in the main analysis of the clinical benefit rate. Patients in response categories 4-9 should be considered to have a treatment failure (disease progression). Thus, an incorrect treatment schedule or drug administration does not result in exclusion from the analysis of the response and clinical benefit rate.

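### Section 12.1 limits objective response to re-evaluated patients, contradicting Sections 8.7 and 17.5, and Section 17.3 names no ORR denominator

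*Combined protocol and SAP*

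**What the plan says.** ORR is the first secondary objective in Section 3.2. For its analysis, Section 17.3 says only "We will calculate the ORR, CBR, DOR, and OS and corresponding 95% confidence intervals". It names no analysis set.

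Three other sections say who counts for response.

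- **Section 12.1** restricts evaluability for objective response to patients with baseline measurable disease who "have received at least one cycle of therapy, and have had their disease re-evaluated will be considered evaluable for response", and has response classified in these patients. Its one exception is "Patients who exhibit objective disease progression prior to the end of cycle 1 will also be considered evaluable".
- **Section 8.7** states "All patients who initiate protocol treatment will be included in the overall evaluation of response (intent-to-treat analysis". It keeps non-compliant patients, and keeps patients who withdraw "if any protocol therapy was administered prior to withdrawal".
- **Section 17.5** states "All patients included in the study must be assessed for safety, tolerability, and response to treatment, even if there are major protocol treatment deviations", and extends this to ineligible patients. Its outcome list has three early-death categories (5 to 7) and one for unknown (9). It adds "Patients in response categories 4-9 should be considered to have a treatment failure (disease progression".

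On timing, the tumor-assessment footnote to the Section 7.1 calendar puts the first on-treatment scan at day 1 of cycle 4 (week 9), or up to 5 days earlier. It asks for a scan at the end-of-treatment visit if none was obtained in the preceding 6 weeks.

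Sections 12.1, 17.3 and 17.5 are printed a second time after the reference list, with the same wording.

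**The concern.** A patient who dies, deteriorates clinically or withdraws before any repeat evaluation has not responded. Section 12.1 leaves that patient unclassified, while 8.7 and 17.5 keep the patient in. The exclusion depends on what happened after treatment began and is tied to failure, so it works in one direction only.

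The plan expects such patients. Section 12.3.5 has a reporting term for symptomatic deterioration without objective progression, and the 12.1 exception does not cover them.

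The trial is open-label and 17.3 does not say which rule governs. The ORR denominator could therefore be settled after the outcomes are known.

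**Working it through.** **1. The plan's own figure.** No figure is stated for ORR. The only design figure is the sample size in 17.2: 106 patients, medians 2.9 and 4.4 months, one-sided 0.10, power 80%, 24 months' accrual and 12 months' follow-up.

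- Hazard ratio = 2.9/4.4 = 0.659.
- Schoenfeld events = 4(1.2816 + 0.8416)²/(ln 0.659)² = 18.03/0.1738, or 104 rounded up.
- Under exponential PFS and uniform accrual, the event probability is 0.990 (control) and 0.961 (combination), mean 0.976.
- N = 104/0.9755 = 106.6. Power at 106 is 79.9%.

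The stated size reproduces. It rests on PFS, so the ORR rule does not touch it.

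**2. The rules side by side, for treated patients with baseline measurable disease.**

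| Patient | 12.1 | 8.7 | 17.5 |
|---|---|---|---|
| Objective progression before end of cycle 1 | in | in | in, failure |
| Stops before week 9 after at least one cycle, end-of-treatment scan done | in | in | in |
| Dies with no repeat evaluation | out | in | in, failure (5 to 7) |
| Deteriorates or withdraws with no repeat evaluation | out | in | in, failure (for example 9) |

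The last two rows are the conflict. The 17.5 failure rule stands in a paragraph that opens with clinical benefit rate, but the closing sentence of that paragraph covers response as well.

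**3. Size.** Let n be the treated patients in an arm, r the responders and k the patients with no repeat evaluation. None of the k can be a responder. All-treated ORR is r/n and the 12.1 ORR is r/(n - k). Their ratio is n/(n - k) = 1/(1 - u), with u = k/n.

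n = 53 comes from 17.2, taking every patient in the arm as treated. The values of r and k are assumptions.

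| k (u) | Ratio | r = 11 | r = 16 | r = 21 |
|---|---|---|---|---|
| 0 | 1.00 | 20.8% | 30.2% | 39.6% |
| 3 (6%) | 1.06 | 22.0% | 32.0% | 42.0% |
| 5 (9%) | 1.10 | 22.9% | 33.3% | 43.8% |
| 8 (15%) | 1.18 | 24.4% | 35.6% | 46.7% |
| 11 (21%) | 1.26 | 26.2% | 38.1% | 50.0% |

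For r = 16, the Clopper-Pearson 95% interval is 18.3% to 44.3% on 53 patients, and 23.6% to 54.4% on 42.

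**The case against.** **Section 12.1 defines a term, not the ORR denominator.** It never names ORR. One can read it as describing a subset, with 8.7 and 17.5 governing the rate. This stands in part: 12.1 is a competing rule and not the declared ORR set. But it says response is classified in the evaluable patients, and neither 17.3 nor any other section says which rule prevails.

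**Fewer patients are lost than it seems.** A reader might infer that anyone who stops before week 9 drops out. The documents do not support that. The end-of-treatment scan and the cycle 1 exception keep some early stoppers. Section 8.7 also lets combination patients with toxicity to one drug continue the other with scheduled scans. The one-cycle condition may exclude few, since dosing is on day 1. Those lost are the patients with no post-baseline evaluation at all.

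**Early PFS events do not measure the loss.** Under the design medians and exponential PFS, 1 - exp(-ln 2 × 2.07/median) gives 39% (control) and 28% (combination) with an event by week 9. These figures include radiographic progression, and such patients have been re-evaluated and stay in the 12.1 denominator.

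**A biased treatment comparison is a further inference.** With 16/53 in both arms but 3 non-evaluable in one and 8 in the other, 12.1 would show 32.0% against 35.6%, a gap of 3.6 points. Unequal loss is assumed there. The ORR objective is not worded as a comparison, and 17.3 plans estimates with intervals and no between-arm ORR test.

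**An all-randomised denominator goes beyond the plan.** Section 6.1 takes a randomised patient who is not treated within the allowed time off the study, and 8.7 starts from treated patients despite its intent-to-treat label.

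**Conclusion.** The contradiction is real and unresolved: one section leaves unclassified the early failures that two others count. Applying 12.1 can only raise ORR. With 16 of 53 responding, the rise is from 30.2% to between 32.0% and 38.1% for 3 to 11 non-evaluable patients, or 1.8 to 7.9 percentage points. The direction follows from the rule itself. The size rests on an assumed response rate and an assumed non-evaluable count, neither of which the documents give.

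The shift lies well inside the confidence interval of a single arm and concerns a secondary endpoint. It does not show that ORR will be inflated, because 12.1 may not be the rule used, and it does not establish a false difference between arms.

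**What to change.** In 12.1 and 17.3, state that the main ORR analysis uses all patients who start protocol treatment, as in 8.7, by assigned arm. Count patients without a post-baseline assessment as non-responders, in line with 17.5. Keep the 12.1 response-evaluable set as a sensitivity analysis, and report the number non-evaluable per arm with the reason. Make the same change in the second copy of 12.1 and 17.3 after the reference list.

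The separate four-week rule for clinical benefit rate in 17.5 concerns another endpoint. Changing that rule alone would leave the 12.1 wording in place.

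The cost is a wording change with no extra patients or assessments. The reported ORR will be slightly lower than under 12.1.
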